8.3.2 APACHE II severity of disease score

APACHE II (Acute Physiology And Chronic Health Evaluation) records various parameters grouped in vital signs, oxygenation, chemistry and hematology; in addition age and Glasgow Coma score is part of the APACHE II score ([Knaus et al 1985](#)) ([Appendix 4](#)). The worst value for each parameter in the last 24 hours will be entered in the CRF, with parameters recorded, if possible, at the same time at every visit for a patient (i.e. morning, afternoon or evening) and upon significant clinical changes. Parameters for APACHE II will be recorded at screening/baseline, Day 2 and then every other day until Day 29 for hospitalized participants irrespective of ICU submission. The score will be recorded only for the screening/baseline visit in the CRF.

Mean arterial pressure (MAP) may either be directly measured or calculated from the diastolic and systolic blood pressure (per medical judgement).

For oxygenation variables, where patients have an arterial line sited an arterial blood sample should be used. In patients, without an arterial line sited should have either an arterial, or equivalent measurement (eg capillary blood gas). In the case, where an arterial sample is not indicated or feasible clinically, a venous blood gas sample can be used and the PaO₂ estimated (per medical judgement, see [Table 16-4](#) for guidance on estimation of PaO₂). For a given patient the same methodology to obtain the APACHE II parameters should be utilized throughout the study where clinically feasible/indicated.

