6.1.4 Sensitivity analysis for primary objective

The combined APACHE II endpoint as described in the estimand above is assumed to follow a normal distribution.

The primary endpoint will be analyzed by an analysis of covariance model including treatment group and the three stratification factors as factors and baseline APACHE-II score as a covariate. The analysis will be performed on the PD analysis set 2. The mean differences of MAS825 vs placebo will be reported with 90% confidence intervals (CIs). The 1-sided p-value for the overall treatment factor will be reported.

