6.1.7 Missing data

Missing data for the APACHE II score will be handled as follows:

- Missing values for age at screening will be replaced by using the stratification information assigning 3 points to participants up to 65 years (≤ 65 years) and 5 points to participants above 65 years.
- Missing information on acute renal failure status: use Serum Creatinine values without renal status information.
- Subscores of the Glasgow Coma Score (i.e. responses to Best Eye Response, Motor Response, Verbal Response) scored as “untestable”, “unknown” or missing will be replaced by the last available actual score. The response “untestable” is selected if the patient is unconscious (e.g. through sedation in case of mechanical ventilation).
- Missing values in any of the other parameters required for the derivation of the APACHE II score will be replaced by the last available assessment, as long as data is not carried forward by more than 4 days.

For a given visit, these missing data rules will only be applied if for at least one of the parameters contributing to the APACHE II score a value at this visit was reported.

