6.1.9 Derivation of the primary estimand

The primary estimand, referred to as the “**combined APACHE II score**”, will be derived as follows from the APACHE II scores after application of the missing data as well as discharge and death handling approaches described above:

- For participants hospitalized at Day 15: APACHE II score at Day 15
- For participants discharged prior to Day 15: APACHE II score at the discharge visit is used

- For participants that died on Day 15 or earlier: highest observed APACHE II score of any of the participants at any time during the trial.
- Imputation for death takes precedence over the imputation of the APACHE II score on day of early discharge.

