6.2 Secondary objectives

6.2.1 Variables

The following variables and corresponding objectives are classified as secondary pharmacodynamic endpoints and will be evaluated for their effect of MAS825 compared with placebo,

- On inflammatory status: Serum C-reactive protein (CRP) levels and ferritin
- On clinical status: Endpoints based on the 9-point ordinal scale:
- Survival without the need for invasive mechanical ventilation at Days 15 and 29 defined by a 9-point ordinal scale score of < 6 points at all time points
- At least one level improvement in clinical status at Days 15 and 29: defined as difference of ≥ 1 in the 9-point ordinal scale score of the screening value – Day 15 or Day 29 respectively.
- Clinical status over time

Missing data

For the clinical status 9-point ordinal scale missing values will be handled as follows:

- For participants who died prior to Day 29: The score for death will be imputed for all visits following the death up to and including Day 29.

For all other participants: LOCF will be applied up to and including Day 127. Following discharge or early discharge LOCF will be applied to all intermediate visits.

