7.2.1 Subject demographics and other baseline characteristics

Screen failures with SAEs

For screen failed participants in case the participant experienced a serious adverse event during the screening phase the following information is captured and listed: demographic information, informed consent, as well as information on SAEs. Inclusion/Exclusion criteria will be summarized.

Disposition

The following disposition status will be summarized as the number and percentage of participants

- who were screened but not randomized (percentage based on all screened participants)
- who were randomized (percentage based on all screened participants)
- who were randomized but not treated (overall and by reason)
- who were discharged prior to day 15 and day 29
- who completed the study until day 15, day 29, day 45 as well as day 127
- who discontinued treatment prior to day 15,
- who discontinued from study (overall and by the primary reason for discontinuation).

The number and percentage of participants included in each analysis set will be tabulated by treatment group. Participants excluded from an analysis sets will be listed with reasons for exclusion (i.e. including both protocol and non-protocol deviations).

Unless otherwise stated any percentages are based on the respective number of randomized participants.

Demographic and Baseline characteristics

Demographic characteristics, including gender, race, ethnicity, age, age categories (<65 and \geq 65 years), height, body weight at screening, body categories (40 to <60 kg, 60 to <80 kg, 80 kg to <100 kg, 100 kg to <120 kg, $\geq=120$ kg), body mass index (BMI), BMI categories (< 30.0 kg/m² and 30.0 kg/m² to 40 kg/m², $\geq=40$ kg/m²) will be summarized with descriptive statistics by treatment and overall.

A stacked barchart illustrating gender, race and ethnicity will be done. Boxplots will be done for all continuous variables in demographics and baseline characteristics.

Body weight and BMI will be also summarized by time point.

Body mass index (BMI) will be calculated using the following formula:

- $BMI = \text{Body weight (kg)} / [\text{Height (m)}]^2$

The Screening visit height measurement will be used for BMI calculations throughout the study.

The number of days between the onset of symptoms to start of treatment will be listed.

The summary of the following baseline disease characteristics will be provided by treatment group:

- Days from the onset of symptom to randomization

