- If “Did the subject experience Severe organ system insufficiency or is immunocompromised ?” is selected as “yes” Chronic Health points will be derived from “Admission Classification”:
 - Medical(non-operative)
 - Emergency post-operative
 - Elective post-operative

If in this scenario none of these conditions is selected the Chronic Health points will be set to 0.

14. Glasgow Coma Score: First each sub-score is scored according to the scoring table below

- Best Eye Response
- Motor Response
- Verbal Response

Then these three subscores are added up to obtain the scoring of the “Total Glasgow Coma Score”. The value included in the APACHE II for Glasgow-Coma-Score is then = 15 – “Total Glasgow Coma Score”.

SDTM Mapping strategy

APACHE II specific mapping strategy: It provides guidance on how the result variables (RSORRES, RSSTRESC, and RSSTRESN) should be populated for the measure. All original results are represented with preferred terminology in RSORRES. This result is then transformed into a standard numeric score in RSSTRESN and a character representation of the standard numeric score in RSSTRESC.

To obtain the total APACHE II score all 14 derived values of RSSTRESN are then added up. If one item is missing the APACHE II score at SDTM level for this visit is missing. Missing data imputation will be implemented at ADAM level.

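### A survivor whose Day 15 or discharge visit is wholly blank gets no primary APACHE II value, even with complete data one to three days old, and leaving the study alive and undischarged before Day 15 has no rule

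*SAP*

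**What the plan says.** Protocol 12.4.4 leaves the handling of missing APACHE II scores, and of missing components, to the SAP.

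SAP 6.1.7 sets rules for components. Glasgow Coma sub-scores take the last available actual score, with no day limit. Most other parameters take the last available assessment if it is no more than 4 days old. A closing condition governs the whole list: "For a given visit, these missing data rules will only be applied if for at least one of the parameters contributing" to the score a value was reported at that visit.

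SAP 6.1.9 builds the primary value from three cases:

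- Still an inpatient: "For participants hospitalized at Day 15: APACHE II score at Day 15".
- Sent home earlier, and still alive on Day 15: "For participants discharged prior to Day 15: APACHE II score at the discharge visit is used".
- Death on or before Day 15, which takes the highest score observed in the trial.

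SAP 6.1.8 derives no score for any visit after the discharge visit. No site-recorded score can stand in. Protocol 8.3.2 says of the score, as distinct from its parameters: "The score will be recorded only for the screening/baseline visit in the CRF". SAP 10.2 adds: "If one item is missing the APACHE II score at SDTM level for this visit is missing"; imputation follows at the analysis-data stage.

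The sensitivity analysis in SAP 6.1.4 keeps the same model and changes the population: "The analysis will be performed on the PD analysis set 2".

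**The concern.** The 4-day limit already decides how old a value may be. The extra condition makes the result depend on something else, namely whether anything at all was written down on the target day. Two participants with identical, complete Day 14 data can end differently: one with a single Day 15 temperature gets a full score, the other gets nothing. The Day 14 data are equally informative about both.

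The second gap is the participant who leaves the study alive before Day 15 without hospital discharge. None of the three cases in 6.1.9 describes this person. Protocol section 8 asks for the Day 15 assessments at premature study discontinuation, but the SAP does not say whether they supply the primary value.

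The SAP states no rule for a missing response in the ANCOVA. The natural inference is that both kinds of participant drop out of the primary analysis while remaining in the safety analysis set. That costs some precision and, if the losses are informative and differ between arms, some bias. With no written rule for study exit, the handling could be settled after data have been seen.

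**Working it through.** **1. Tracing the rules.**

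| Survivor's situation | 6.1.7 carry-forward | Source in 6.1.9 | Primary value |
|---|---|---|---|
| In hospital, Day 15 partly recorded | open | Day 15 | full score, if the gaps can be filled within the limits |
| In hospital, Day 15 wholly blank, Day 14 complete | closed | Day 15 | none |
| Discharged before Day 15, discharge visit wholly blank | closed | discharge visit | none; 6.1.8 bars a returned Day 15 score |
| Left study alive, undischarged, before Day 15 | not addressed | no case | undefined |

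Age and chronic health points are taken at screening (SAP 10.2), so I do not count them as reported at the visit. SAP 4.2 lets unscheduled data feed carry-forward, but the 6.1.7 condition still applies.

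**2. Would usable data exist?** Scheduled days are 1 (baseline), 2, 4, 6, 8, 10, 12 and 14 (protocol Table 8-1). Before a blank Day 15, Day 14 is 1 day old and Day 12 is 3 days old, both inside the limit; Day 10 is 5 days old and outside. For discharge on Day 14, Days 10 and 12 qualify; on Day 9, Days 6 and 8; on Day 3, Days 1 and 2. Every target day from 3 to 15 has at least two earlier scheduled assessments within 4 days.

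**3. The plan's power.** Inputs from protocol 12.9.1: 60 per arm, difference 3.6, SD 9.2, one-sided alpha 0.10. The noncentrality is 3.6 / (9.2 × √(2/60)) = 3.6 / 1.680 = 2.143 on 118 degrees of freedom. Noncentral-t power is 80.4% (normal approximation 80.6%), so the stated 80% reproduces.

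**4. Power after loss (rates assumed, equal in both arms).**

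| Analysed per arm | Lost per arm | Power |
|---|---|---|
| 60 | 0 | 80.4% |
| 59 | 1 | 79.8% |
| 58 | 2 | 79.3% |
| 57 | 3 | 78.8% |

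The protocol states no allowance for missing values, and drug supply caps the MAS825 arm at 60.

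**5. Bias (all inputs assumed).** If a fraction f of an arm is lost and their true mean lies g points below the full-arm mean, the observed arm mean is too high by g × f/(1−f). The contrast is biased by the difference of this quantity between arms.

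- Equal f and equal g: 0.
- f of 2% versus 5%: 0.05/0.95 − 0.02/0.98 = 0.0526 − 0.0204 = 0.0322. With g = 4.6 (half an SD) the bias is 0.15 points; with g = 9.2 (one SD), 0.30 points. That is 4% to 8% of 3.6.
- f of 5% in both arms, g = 4.6 in one and 9.2 in the other: 4.6 × 0.0526 = 0.24 points, or 7% of 3.6.

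**6. Two side checks.** SAP 6.1.2 plans to summarise the actual Day 15 score of early-discharged participants, which 6.1.8 says is not derived. In SAP 10.2.1, a PaO2 reported only as below 55 mmHg is set to 55 and falls in the 55–60 row (3 points), although the table has its own row for below 55 (4 points). The difference is 1 point per affected value.

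**The case against.** The strongest reply is that the case is rare. A visit counts as blank only if no temperature, pressure, heart rate, respiratory rate, blood gas, chemistry, haematology or coma score was recorded. Protocol Table 8-1 expects a Day 15 visit for all patients and Day 15 assessments on the day of discharge. For study exit, protocol 9.1.1 does not count people as withdrawn unless they withdraw consent, and loss to follow-up of an inpatient is hard to picture, so what remains is mainly consent withdrawal in hospital. All of this stands and limits the size.

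It can also be said that the condition is a deliberate choice: it completes an attended visit and declines to build a whole visit from older data. That is a fair reason to be wary of carry-forward, which may overstate severity in someone recovering. It is not a reason to have no value at all when baseline and Day 2–14 scores are available to impute from. Simply deleting the condition would moreover let Glasgow Coma sub-scores be carried into a blank visit with no day limit.

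Four stronger readings are tempting and are not supported:

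- A reader might infer that early discharge in general leaves the endpoint missing. It does not; 6.1.9 covers ordinary discharge.
- A reader might infer that these participants vanish from the report, because SAP 7.2.1 promises only that "Participants excluded from an analysis sets will be listed with reasons for exclusion" and they stay in the safety set. The same section tabulates study discontinuation by primary reason, so exits are visible; blank visits are not.
- A reader might infer inconsistency from the 9-point scale, where, for participants who did not die before Day 29, "LOCF will be applied up to and including Day 127" with no such condition. That scale is a single item obtainable by telephone, whereas APACHE II needs 14, so different rules are reasonable.
- A reader might infer that no analysis uses the earlier scores. Part of SAP 6.1.10 is blacked out, and its analyses 2–4 use scheduled scores to Day 29, so a supportive analysis may keep these participants. It would not define their primary value.

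**Conclusion.** The point holds in a limited form. On the visible text of SAP 6.1.7 to 6.1.9, a survivor with a wholly blank Day 15 or discharge visit has no primary value despite recent complete data, and a participant who leaves the study alive and undischarged before Day 15 has no defined value. The first is a stated rule that gives a worse result than an inexpensive alternative; the second is mostly missing detail.

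The documents give no frequency. If 1 to 3 of 60 per arm were affected, power would fall by 0.6 to 1.6 percentage points. A conclusion that the treatment contrast is biased would go too far: bias is zero when the loss and its relation to outcome match between arms, and it was 0.15 to 0.30 points in the unequal cases tried. Omission from the ANCOVA is itself an inference. Priority: minor to moderate.

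**What to change.** 1. In SAP 6.1.7 and 6.1.9, state that a survivor with a wholly blank Day 15 or discharge visit, or who leaves the study alive before Day 15 without discharge, has the primary value filled by a pre-specified method, for example multiple imputation from baseline and Day 2–14 scores. Alternatively, remove the one-parameter condition for these two visits, with the 4-day limit applied to every component, including Glasgow Coma sub-scores. Use whichever approach is not primary as a sensitivity analysis.
2. Report by arm how many participants had no observed primary visit and how each value was filled.
3. Exempt the 6.1.2 descriptive summary from 6.1.8, so that the Day 15 scores of early-discharged participants can be derived for it.
4. Minor: in 10.2.1, score a PaO2 reported as below 55 in the table's own row (4 points).

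The cost is SAP wording, programming and one added sensitivity analysis, with no new data collection. Multiple imputation would rest on a missing-at-random assumption, which should be stated.

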6.1.8 Handling of discharge and death

For the APACHE II score,

- in case a participant is discharged before Day 29 it will not be derived for any visits after the discharge visit (i.e. the last APACHE II score will be derived on the day of discharge).
- In case a participant dies no APACHE II score will be derived starting from the day of death.

6.1.9 Derivation of the primary estimand

The primary estimand, referred to as the “**combined APACHE II score**”, will be derived as follows from the APACHE II scores after application of the missing data as well as discharge and death handling approaches described above:

- For participants hospitalized at Day 15: APACHE II score at Day 15
- For participants discharged prior to Day 15: APACHE II score at the discharge visit is used

- For participants that died on Day 15 or earlier: highest observed APACHE II score of any of the participants at any time during the trial.
- Imputation for death takes precedence over the imputation of the APACHE II score on day of early discharge.

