2.2 Secondary estimands

Not applicable

3 Study design

This is a Phase 2, randomized, placebo -controlled, participant and investigator blinded, multi-center study to assess the efficacy and safety of MAS825 for the treatment of SARS-CoV-2 infected patients with COVID-19 pneumonia and impaired respiratory function ([Figure 3-1](#)).

Figure 3-1 Study design

* End points calculated on day of discharge in patients discharged prior to Day 15

The study consists of five parts:

1. **Screening / Baseline / Treatment** (Day -1 to 1): lasts up to a maximum of 24 hours and comprises a screening / baseline assessment. This visit will be used to confirm that the study inclusion and exclusion criteria are met and serves as baseline assessment prior to randomization. Baseline blood tests will be performed in all patients; those who screen fail because of study inclusion / exclusion criteria (e.g., serum CRP, liver function tests), will not undergo randomization.

Eligible patients will receive a single i.v. infusion of CCI MAS825 or placebo on Day -1 to 1 and will be observed until Day 15. Patients will be randomized as soon as possible, but within a maximum of 24 hours after screening in a 1:1 ratio to receive either treatment with MAS825 or placebo in addition to SoC. Randomization will be stratified according to the following, all of which may influence outcome in COVID-19:

- age (\leq 65years, $>$ 65years)
- administration of any anti-viral therapy (e.g., hydroxychloroquine, chloroquine, convalescent plasma, remdesivir, faripivavir, ritonavir, lopinavir) as SoC (yes / no)
- presence of \geq 1 of the following comorbidities: diabetes, hypertension, cardiovascular disease, chronic lung disease (yes / no)

2. **Treatment period** (Day 2-15): Study assessments to be conducted every 2 days for hospitalized patients. If patients are discharged from the hospital prior to Day 15, assessments on the day of discharge should be performed according to the schedule listed under Day 15 and patient should return to the site for the Day 15 assessment (all other visits between discharge and Day 15 can be omitted). If a hospital visit is not possible at Day 15, then home nursing services may be used to support this last visit where these are available in accordance with local guidelines and should include all possible assessments (e.g. oxygen saturation with portable monitors). In case home nursing is not possible, patients will be contacted by phone on day 15.

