6.1.1 Variable

The primary clinical question of interest is: What is the effect of MAS825 compared with placebo in SARS-CoV-2 infected patients with COVID-19 pneumonia and impaired respiratory function on APACHE-II severity of disease score taking into account early discharge from hospital or death but regardless of investigational treatment discontinuation?

The justification for the primary estimand is that it will capture the combined effect of investigational treatment in participants who remain in hospital for 14 days, the effect on early discharge within 14 days and the effect on death rate within 14 days, in a manner than reflects clinical practice. In this document the primary estimand will be referred to as the “**combined APACHE II score**”.

The primary estimand is described by the following attributes:

- **Population:** SARS-CoV-2 infected patients with COVID-19 pneumonia and impaired respiratory function.
- **Endpoint:** APACHE II severity of disease score on Day 15 or on day of discharge (whichever is earlier) with worst case imputation for death. Participants who die on Day 15 or earlier will be assigned the highest observed APACHE II score of any of the participants at any time during the trial. Note this imputation for death takes precedence over the APACHE II score on day of discharge.
- **Treatment of interest:** the randomized treatment (the investigational treatment MAS825 or placebo).
- **Handling of remaining intercurrent events:** Treatment discontinuation for any reason will be ignored and thus follow a treatment policy strategy i.e. participants who discontinue treatment will be treated in the same manner as those that continue the treatment as planned.
- **Summary measure:** The difference in variable means between treatments.

APACHE II scores are on a range between 0 and 71 points, however, in practice it is rare for any patient to accumulate more than 55 points. A decrease in the APACHE II score is considered a favorable outcome.

The APACHE II scores are derived from a number of different clinical endpoints according to the scoring table as outlined in (Knaus et al., 1985) and listed in the Appendix. The handling of missing data is described in [Section 6.1.7](#).

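### Readmission after early discharge: the primary value stays at the discharge-day APACHE II score by implication only, and invasive ventilation between scored days can count as ventilation-free survival

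*SAP*

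**What the plan says.** **Primary endpoint.** Protocol 2.1 and SAP 6.1.1 define it as "APACHE II severity of disease score on Day 15 or on day of discharge (whichever is earlier) with worst case imputation for death". SAP 6.1.9 turns this into rules. One bullet reads "For participants hospitalized at Day 15: APACHE II score at Day 15". The next reads "For participants discharged prior to Day 15: APACHE II score at the discharge visit is used". SAP 6.1.8, which is applied first, says that "in case a participant is discharged before Day 29 it will not be derived for any visits after the discharge visit". One override is stated: "Imputation for death takes precedence over the imputation of the APACHE II score on day of early discharge". SAP 6.1.2 adds a descriptive summary, for participants discharged early, of the discharge score beside the actual Day 15 score where both exist.

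**Ventilation-free survival.** SAP 6.2.1 has this "defined by a 9-point ordinal scale score of < 6 points at all time points", and SAP 6.2.2 counts responders up to Day 15 and up to Day 29. After discharge, Protocol section 3 (treatment period) says "all other visits between discharge and Day 15 can be omitted", with a matching allowance before Day 29. SAP 6.2.1 fills intermediate visits after discharge by LOCF. Under Protocol 8.3.3 each ordinal score is the worst status of a single calendar day.

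Neither document mentions readmission in its visible text.

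**The concern.** Two gaps follow when a discharged participant returns to hospital.

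First, the two 6.1.9 bullets are not mutually exclusive. A programmer has to combine them with 6.1.8 and the endpoint wording to find the intended value. That value, the discharge score, does not register a relapse short of death, although death after discharge does override it. The plan's only look at the later score (6.1.2) conflicts with 6.1.8, which derives no score after discharge.

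Second, the ventilation endpoint is cumulative in intent but is read only at scored days. Invasive ventilation in an unscored stretch after discharge is not seen, although it is exactly the event that the endpoint is meant to count. Whether such a participant is a success or a failure can depend on whether the site happened to carry out optional visits. The Kaplan-Meier display in SAP 6.2.5 would be affected if its events come from the same scores.

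**Working it through.** **The plan's own figure.** Inputs from Protocol 12.9.1: 60 per arm, difference 3.6, SD 9.2, one-sided alpha 10%.
- Standard error = 9.2 × √(2/60) = 1.68.
- Power = Φ(3.6/1.68 − 1.282) = 80.6% (80.4% with the noncentral t on 118 df). The stated 80% reproduces, and a readmission rule would not change it.

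**Trace 1, primary endpoint.** Discharged Day 6, readmitted Day 9, ventilated on Day 15.
1. The participant meets both 6.1.9 bullets.
2. The earlier of Day 15 and day of discharge is Day 6.
3. Under 6.1.8 no Day 15 score exists for the first bullet to use.
4. The participant is alive, so the death override does not apply.
5. The primary value is the Day 6 score. On Day 15 the ordinal score is at least 6, so the same participant fails ventilation-free survival.

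**Trace 2, ventilation-free survival to Day 15.** Discharged Day 6, ventilated only on Days 9–12.
1. The scheduled visits on Days 8, 10, 12 and 14 can be omitted; LOCF gives them the last score.
2. If the Day 15 score is below 6, no score reaches 6 and the participant is a responder.
3. If the site did score Days 10 and 12, those scores would be at least 6 and the participant would be a failure.

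**Trace 3, ventilation-free survival to Day 29.** Discharged Day 12, readmitted Day 17, ventilated Days 18–26, next contact Day 29. With interim visits omitted, this is a success. With inpatient scoring on Days 19, 21, 23 and 25, it is a failure.

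**Days without a score if interim visits are omitted.** Before Day 15 this is 14 minus the discharge day:

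| Discharge day | 4 | 6 | 8 | 10 | 12 |
|---|---|---|---|---|---|
| Unscored days before Day 15 | 10 | 8 | 6 | 4 | 2 |

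Between Day 15 and Day 29 there are 13 (Days 16–28).

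**Size, primary endpoint.** Let D be the Day 15 score minus the discharge score. The documents give neither D nor a readmission rate, so both are assumptions. Each case moves an arm mean by D/60:

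| D | Shift per case | Share of 3.6 |
|---|---|---|
| 5 | 0.08 | 2.3% |
| 10 | 0.17 | 4.6% |
| 15 | 0.25 | 6.9% |
| 20 | 0.33 | 9.3% |

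For a net excess of 1 to 4 cases in one arm and D of 10 to 15, the treatment difference shifts by 1 × 10/60 = 0.17 to 4 × 15/60 = 1.00 points. Taking the Day 15 score as the benchmark:
- Excess in placebo, true difference 3.6: power falls from 80.6% to between 77.7% and 60.5%.
- Excess in MAS825, no true effect: one-sided type I error rises from 10% to between 11.9% and 24.6%.
- Equal numbers with equal D in both arms: no shift.

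**Size, ventilation-free survival.** One missed episode is 1/60 = 1.7 percentage points of an arm.

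**The case against.** The strongest reply is that the discharge score is the estimand. A reader might infer that the primary endpoint is meant to show status at Day 15, so that using an earlier score is an error. The documents do not support that. The definition takes the earlier of the two days, and Protocol 2.1 names early discharge within 14 days as a component to be captured. The participant also gets the score actually measured at discharge, not a fixed recovery value, so it would be too strong to say that relapse is scored as recovery. This part of the objection stands. What remains is that readmission is unaddressed, the bullets overlap, and 6.1.2 and 6.1.8 disagree.

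A reader might also infer that ventilation during any readmission goes unseen. That too is stronger than the text allows:
- The Table 8-1 follow-up heading ties site assessments every 2 days to being hospitalized, and Protocol 8.3.2 and 8.3.3 do the same for APACHE II and the ordinal scale. A readmitted patient can be read as covered.
- Omitting visits is permitted, not required, and LOCF fills only missing values.
- Ventilation on Day 15, Day 29 or any scored visit is caught.

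However, footnote 4 of Table 8-1 requires the full schedule only if the patient remains hospitalized, so the text is ambiguous for a return to hospital.

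Telephone contacts already obtain respiratory history and adverse events (Table 8-1, footnotes 3 and 4), and inpatient hospitalization is an SAE criterion (Protocol 10.1.2). These data exist, but no visible rule carries them into the endpoint. SAP 4.2 keeps unscheduled-visit data out of by-visit analyses. Its LOCF exception names the APACHE II, SAPS II and SOFA scores, not the ordinal scale.

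Finally, part of the supportive analyses (SAP 6.1.10) and the exploratory section are redacted, so whether they address this cannot be judged.

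**Conclusion.** The point holds in a limited form. For the primary endpoint the written rules give one value, the discharge-day score, but only by inference across sections. Nothing inferential in the visible text tests how far relapse after discharge would change the result. For ventilation-free survival the rules can return the wrong answer: a participant who was invasively ventilated can be counted as a success when the episode falls between scored days and interim visits were not done.

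The size is unknown and may be small. The figure of 0.08 to 0.33 points per case rests on an assumed gap of 5 to 20 points. The power and type I error ranges rest further on an assumed imbalance between arms, for which the documents give no reason in a blinded trial. They describe departure from a Day 15 benchmark, not bias in the estimand that the plan chose. A reader should not conclude that either arm is favoured.

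**What to change.** 1. **SAP 6.2.1.** Count any invasive ventilation recorded up to Day 15 or Day 29 as an event, from respiratory-status, SAE, procedure or phone-contact records, whether or not a scored visit falls within it. State that LOCF does not override it.
2. **SAP 6.1.8 and 6.1.9.** State the readmission rule so that the two bullets are mutually exclusive. Allow the Day 15 score to be derived for readmitted participants, and add a sensitivity analysis of the primary endpoint that uses it. Align 6.1.8 with the Day 15 summary in 6.1.2.
3. **Protocol Table 8-1, footnotes 3 and 4.** Clarify that the schedule for hospitalized patients applies on readmission to the study hospital, and record readmission and ventilation dates at the Day 15 and Day 29 contacts.

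Items 1 and 2 cost a few sentences in the SAP and one extra model. Item 3 changes protocol text and so needs a written amendment under Protocol 14.1. Sample size and the primary estimand stay as they are; replacing the estimand would be a separate, more debatable change to Protocol 2.1. A small downside is that data may be incomplete when readmission is to a non-study hospital.
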